- c A trephine (biopsy) is to be collected for baseline. A bone marrow biopsy collected per SOC within 30 days of randomization can be considered the screening sample, and shipped to central laboratory. This procedure must be performed prior to the first dose of study treatment at the latest. An aspirate sample must be collected at the screening visit for blast evaluation, MRD assessment, biomarker studies, baseline for response assessment and biobanking. It is preferred that bone marrow aspirate samples are obtained at the time of bone marrow (trephine) biopsy. Conventional cytogenetics to be tested per institutional standards.
- d Hematology analytes to be assessed at screening are provided in Table 7.
- e ABO/Rh type, antibody screen, DAT, and extended RBC phenotyping (including minor antigens such as CcDEe, Cw, MNSs, Kk, FyaFyb, and JkaJkb) must be performed for each participant. Red blood cell genotyping instead of extended RBC phenotyping is acceptable for any patient. Red blood cell genotyping (instead of an extended RBC phenotyping) must be performed if a participant received any RBC or whole blood transfusion within the previous 3 months (unless the laboratory has availability for special techniques for performing phenotyping for participants with a recent transfusion). Results must be available before the first dose of magrolimab.
- f Refer to Exclusion Criteria 13 and Other Laboratory Measurements in Table 7.

Table 3. Schedule of Assessments - Treatment Period-Azacitidine Dosing and Study Assessments

Visit Window (Days)	Cycle (28-day Cycles)																					
	1							2							3+							
	None		± 3					± 3							± 3							
Cycle Day	1	2	3	4	5	6	7	1	2	3	4	5	6	7	1	2	3	4	5	6	7	
PRO assessment ^a	X							X							X							
CBC with differential, platelets, reticulocytes ^b	X							X							X							
Serum or plasma chemistry ^b	X							X							X							
Bone marrow biopsy and aspirate for biomarker studies ^c															X ^{d,e}							
Bone marrow aspirate biopsy for MRD monitoring, cytogenetics, and response assessment ^{d,f}															X Q2C, Q3C ^e							
Vital signs ^g	X	X	X	X	X	X	X	X	X	X	X	X	X	X	X	X	X	X	X	X	X	X
Symptom-directed physical examination ^b	X							X							X							
Adverse events	X	X	X	X	X	X	X	X	X	X	X	X	X	X	X	X	X	X	X	X	X	X
Blood transfusion	X	X	X	X	X	X	X	X	X	X	X	X	X	X	X	X	X	X	X	X	X	X
Concomitant medications	X	X	X	X	X	X	X	X	X	X	X	X	X	X	X	X	X	X	X	X	X	X
Azacitidine ^h	X	X	X	X	X	X	X	X	X	X	X	X	X	X	X	X	X	X	X	X	X	X

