5.1.9.1. FACT-Anemia

The FACT-Anemia questionnaire is a 47-item instrument used to assess anemia- and fatigue-related quality of life for patients with cancer and chronic disease. A sample is provided in Appendix C. This instrument consists of 5 subscales, including physical well-being, emotional well-being, functional well-being, social well-being, and anemia symptoms. Each subscale measures items on a 5-point Likert scale from 0 to 4, where 0 = not at all and 4 = very much. The FACT-Anemia instrument has demonstrated good validity and reliability in the general population as well as in patients with cancer {Cella 2012, Revicki 2013}.

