FACT-Anemia Response Rate: The FACT-Anemia response rate is defined as the proportion of participants who showed clinically meaningful improvement in health-related quality of life (HRQoL) based on the score from the FACT-Anemia instrument prior to initiation of any new anticancer therapy, including SCT.

Duration of RBC Transfusion Independence: The duration of RBC transfusion independence is measured from the time the assessment criteria are first met for RBC transfusion independence until RBC transfusion dependence again (including assessments post SCT) or death. Those who are not observed to have one of these events will be censored at the date of their last response assessment with evidence of no RBC transfusion dependence again.

Transplantation Rate: The transplantation rate is defined as the proportion of participants who initiate transplant therapy for MDS after randomization.

Time to First Transplant: Time to first transplant is defined as the time from randomization to the initiation of first transplant therapy for MDS. Participants who are not observed to initiate transplant therapy will be censored at their last known alive date or death date if the patient died.

RBC Transfusion Independence Irrespective of RBC Transfusion-Dependence at Baseline: The RBC transfusion independence irrespective of RBC transfusion-dependence at baseline is the proportion of participants who have a 56-day or longer period with no RBC transfusions at any time between randomization and initiation of any new anticancer therapy, including SCT, among all participants irrespective of RBC transfusion-dependence at baseline.

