3.8.2. Analysis Visit Windows

Subject visits might not occur on protocol-specified days. Therefore, for the purpose of analysis, observations will be assigned to analysis windows. The analysis windows for lab are provided in Table 3-1.

		Visit Window Study Day		
Analysis Visit	Nominal Study Day	Lower Limit	Upper Limit	
Baseline			1 ^a	
Week 1	8	1 ^b	11	
Week 2	15	12	18	
Week 3	22	19	25	
Week 4	29	26	32	
Week 5	36	33	39	
Week 6	43	40	46	
Week 7	50	47	53	
Week 8	57	54	63	
Week 10	71	64	77	
Week xx	xx*7+1	(xx-1)*7+1	(xx+1)*7	

Table 3-1.Analysis Visit Windows for Lab By-visit Summaries

a Prior to first dose date time.

b Post first dose date time.

The analysis windows for PRO are provided in Table 3-2.

 Table 3-2.
 Analysis Visit Windows for By-visit Summaries of PRO assessments

Analysis Visit	Nominal Study Day	Visit Window Study Day	
		Lower Limit	Upper Limit
Baseline			1
Week 4	29	2	42
Week 8	57	43	70
Week 12	85	71	98
Week xx	xx*7+1	xx*7-13	xx*7+14

For any data relating to unscheduled visits, the following will be made:

- An unscheduled visit prior to the first dosing of any study drug will be included in the calculation of the baseline value, if applicable.
- Unscheduled visits after the first dosing of any study drug will be included in determining the maximum postbaseline toxicity grade and anti-magrolimab antibody status.
- Response assessments and PRO assessments performed at unscheduled visits after the date of randomization will be included in the analyses of the efficacy endpoints and the PRO related endpoints, respectively.

3.8.3. Selection of Data in the Event of Multiple Records in an Analysis Visit Window

If multiple valid, nonmissing measurements exist in an analysis window, records will be chosen based on the following rules if a single value is needed:

- For baseline, the last nonmissing value on or prior to the first dosing date of study drug (and prior to first dosing time) will be selected, unless specified differently. If there are multiple records with the same time or no time recorded on the same day, the baseline value will be the arithmetic average of the measurements for continuous data, or the measurement with the lowest severity for categorical data.
- For postbaseline values:
 - The record closest to the nominal day for that visit will be selected.
 - If there are 2 records that are equidistant from the nominal day, the later record will be selected.

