Progression-free Survival: PFS is defined as the time from randomization to the date of documented disease progression (including treatment failure by IWG criteria or relapse after PR/CR), or death from any cause, whichever occurs first. Response assessments and deaths post SCT will be included in the analysis. Those who are not observed to have one of these events will be censored at their last response assessment date with evidence of no disease progression/relapse. If patients start taking new anticancer therapies (excluding SCT) before disease progression (including treatment failure by IWG criteria or relapse after PR/CR) or death, PFS will be censored at the last response assessment on or before the initiation of the new anticancer therapies. Patients will be censored at the date of randomization if no response assessment performed after randomization and the patients didn't die.

FACT-Anemia Response Rate: The FACT-Anemia response rate is defined as the proportion of patients who showed clinically meaningful improvement in health-related quality of life (HRQoL) based on the score from the FACT-Anemia instrument on or prior to initiation of any new anticancer therapy, including SCT {Cella 2002}. The minimal clinically meaningful difference of 7.0 as suggested in the referenced literature will be used as cutoff for clinically meaningful improvement. Patients, who are randomized but have no baseline or no postbaseline FACT-Anemia questionnaire assessment or receive any new anticancer therapy including SCT prior to achieving the FACT-Anemia response, will be considered as non-responders.

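### FACT-Anemia response has no fixed visit, confirmation rule or calendar limit, so chance responses build up with the number of forms and favour the arm observed longer

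*SAP*

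**What the plan says.** SAP Section 6.2.1 counts improvement "based on the score from the FACT-Anemia instrument on or prior to initiation of any new anticancer therapy, including SCT" and sets the threshold: "The minimal clinically meaningful difference of 7.0 as suggested in the referenced literature will be used as cutoff for clinically meaningful improvement". Patients without a baseline or a postbaseline form are non-responders, and so are those who "receive any new anticancer therapy including SCT prior to achieving the FACT-Anemia response, will be considered as non-responders". Protocol Section 8.4 uses the same open window and gives no cutoff, visit or confirmation rule.

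Forms are due on Day 1 of every 28-day cycle (Protocol Table 3), at end of treatment, and in long-term follow-up before progression or new therapy (Protocol Table 5 and its footnote g). SAP Section 3.8.2 adds that "PRO assessments performed at unscheduled visits after the date of randomization will be included in the analyses of the efficacy endpoints".

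SAP Section 6.2.2.1 analyses the rate like the CR rate, that is, by a stratified Cochran-Mantel-Haenszel test. Nothing adjusts for the number of forms or the time observed. The 8-month criterion in SAP Table 2-3 sets the information fraction only and does not limit when a response may occur. In the testing order of SAP Section 2.1, FACT-Anemia response comes after OS and seven other key secondaries.

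**The concern.** Neither document says in so many words that one form is enough. That is still the operative reading: the SAP speaks of achieving the response before new therapy and asks for nothing after it is achieved. A programmer would code any qualifying form.

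Under that rule a patient with no real change has a fresh chance of passing the cutoff at every form, so the probability of response rises with the number of forms. If one arm completes more forms, its response rate is higher even with no effect on quality of life. The test is reached only after OS, EFS and PFS are significant, and then the experimental arm is probably the one with more forms. A quality-of-life claim could then partly repeat the survival and progression results. Chance responders in both arms would also dilute a real effect.

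The plan is stricter elsewhere. RBC transfusion independence needs 56 days, and hematologic improvement must last at least 8 weeks. This repeated, self-reported endpoint has no such requirement.

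**Working it through.** **The plan's own figure.** No SD, expected rate or power is given for FACT-Anemia response. The nearest stated figure is the 95% power for CR rate, whose test this endpoint borrows. With 174 per arm, 20% vs 39% and two-sided 0.03, the critical value is 2.170. The null SE is √(2 × 0.295 × 0.705/174) = 0.0489 and the alternative SE is √((0.16 + 0.2379)/174) = 0.0478. Power = Φ((0.19 − 2.170 × 0.0489)/0.0478) = 96.0%, in line with the plan.

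**Inputs from the documents.** Cutoff 7.0; one form per 28 days; 260 per arm (520 at 1:1).

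**Assumed inputs.** Independent normal retest error with SD s per form; no true change; exponential time on forms with a control median of 8 months; hazard ratio 0.71 or 0.85 for time on forms. The 0.71 is borrowed from the OS design, since the plan gives no value for time on forms.

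**Step 1: chance response with k forms.** The baseline error is shared by all comparisons, so with e₀ standard normal

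P(response) = 1 − E[Φ(e₀ + 7/s)^k].

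For k = 1 this is 1 − Φ(7/(s√2)); at s = 7 it is 1 − Φ(0.707) = 24%. Numerical integration gives:

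| Retest SD | 4 forms | 8 forms | 12 forms | 24 forms |
|---|---|---|---|---|
| 3 | 14% | 22% | 27% | 36% |
| 5 | 38% | 50% | 58% | 69% |
| 7 | 51% | 64% | 71% | 80% |
| 10 | 60% | 73% | 79% | 87% |

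The level varies widely with s, but in every row it rises with k.

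**Step 2: forms per arm.** A median of 8 months is 8 × 30.4375/28 = 8.7 cycles. At hazard ratio 0.71 the other median is 8/0.71 = 11.3 months, or 12.2 cycles. At s = 7 that is roughly the step from 64% to 71% in the table. Averaged over the whole distribution of time on forms, the gap is about 5 points.

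**Step 3: false wins.** With s = 7, medians 8 and 11.3 months and 90% evaluable, simulated rates are 51.9% and 56.9%. The SE is √(2 × 0.544 × 0.456/260) = 0.0437, so z = 0.050/0.0437 = 1.14. P(Z > 1.96 − 1.14) is about 21%; the simulation gives 20%.

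Other simulated settings, as the share of trials in which the test favours the longer arm at two-sided 0.05:

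- All patients evaluable, s = 3.5 to 10, control median 8 months: about 22–28% at hazard ratio 0.71 and 7–11% at 0.85. Control response is about 30% (s = 3.5) to 65% (s = 10).
- 90% evaluable, s = 4 to 9, control medians 4 to 10 months, medians in the ratio 25.4/18: 19–28%.
- Equal medians: about 2.5%, the nominal rate.
- Control observed longer (8 vs 6 months): about 18%, in favour of control.
- Correlated errors (0, 0.5, 0.8; s = 5, 7, 10): response rates fall, for example from 58% vs 63% to 41% vs 47% at s = 7, but false wins stay at about 25–33%.
- Two-sided 0.02, which applies if the CR test failed: about 14–17% at hazard ratio 0.71 and s of about 7 to 10.

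**Step 4: remedies.** Counting only the first 8 cycle visits gives about 9–13% at hazard ratio 0.71 and control median 8 months (6–18% over the wider grid). One landmark visit, with death or missing as non-response, gives about 10–12%. With 8 forms and s = 5, 7 and 9, chance response is 50%, 64% and 71% on any form, 20%, 31% and 38% on two consecutive forms, and 16%, 24% and 29% on one prespecified form.

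**The case against.** **No figure rests on the plan alone.** The retest error is not given, and chance response runs from 14% to 89% over SD 3 to 12 and 4 to 24 forms. A reader might infer that noise makes most patients responders. The documents do not support that: at a retest SD of 3.5 the rates are about 30% vs 35%. This stands against any statement about the level. It does not touch the direction, which was the same at every SD tried.

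**Follow-up is not unlimited.** Counting stops at new anticancer therapy or transplant, and follow-up forms are limited to the time before progression. That stands. What is missing is a calendar limit.

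**Survival is not time on forms.** Treatment duration, progression and new therapy drive the number of forms, and 0.71 is the OS assumption. At 0.85 the false-win rate is 7–11%. This stands, but a trial that has also won PFS makes longer time on forms plausible.

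**The test is heavily gated.** It is last of eight, and an O'Brien-Fleming boundary applies at the interims. A reader might take 22–28% as the trial's overall chance of a false quality-of-life claim. It is not: it is conditional on reaching the test. Gating lowers how often the problem arises but does not reverse its direction.

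**By-visit PRO summaries are planned.** SAP Section 6.4.2 describes scores over time, which helps interpretation. Those summaries are not the formally tested result.

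**Conclusion.** The concern holds in this limited form. Followed as written, the rule lets chance responses accumulate with the number of forms and biases the comparison toward the arm observed longer. When the test is reached, that is probably the experimental arm.

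Under the assumptions above (retest SD 3.5–10, control median 8 months on forms, no true change), the longer arm wins falsely in about 22–28% of trials at hazard ratio 0.71 and about 7–11% at 0.85, against 2.5% nominal, and somewhat less at alpha 0.02. These are illustrations, because the documents give neither retest error nor time on forms. True worsening would lower the chance response rates.

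The score is also unnamed. The instrument's 47 items scored 0 to 4 give a maximum of 188, of which 7 points is 3.7%. A reader might conclude that the cutoff is trivially small, but that holds only if 7.0 applies to the total. The cited source is, by its title, about fatigue, and SAP Section 6.4.2 lists several derived scores. The documents do not settle which one is meant.

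This is worth correcting but does not threaten the trial's primary conclusions.

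**What to change.** In SAP Section 6.2.1, for the formal test:

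1. Count responses only within a fixed window common to both arms, for example the first 8 months from randomization, or at one landmark visit such as Cycle 7 Day 1. The 8 months would also agree with the follow-up criterion in Table 2-3.
2. Preferably require the gain on two consecutive scheduled forms.
3. Treat death or missing forms in the window as non-response.
4. Name the score to which 7.0 applies, and say whether a gain of exactly 7.0 counts.
5. Keep the any-form rate as a supportive analysis, reported with the number of forms per patient by arm.

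This reduces the bias without removing it. Counting death or missing forms as non-response still reflects time on study, which is why about 9–13% remains with the 8-cycle window at hazard ratio 0.71.

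The cost is SAP wording; no new data are needed. The downside is that improvements that first appear later, or are not sustained, no longer count in the formal test.

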6.2.2. Analysis Methods for Secondary Efficacy Endpoints

Key secondary efficacy endpoints will be tested according to the order specified in Section 2.1, after the superiority for the primary efficacy endpoint OS is established.

6.2.2.1. Objective Response Rate, CR in TP53 Mutant Population, MRD-negative Response Rate, and FACT-Anemia Response Rate

The ORR, CR in TP53 mutant population, MRD-negative response rate, and FACT-Anemia response rate will be evaluated in a similar manner as the CR rate.

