8.7. Analysis of PRO Data

A key PRO endpoint, FACT-Anemia response rate, is defined based on the ITT Analysis Set (see Section 8.3.1). The analysis method is similar to that of the CR rate. Other indices, such as the Functional Assessment of Cancer Therapy-General (FACT-G), FACT Trial Outcome Index-Anemia scale (FACT TOI-An), and FACT Trial Outcome Index-Fatigue (FACT TOI-F), which can be derived from FACT-Anemia with published minimally clinically meaningful difference, will also be analyzed {[Cella 2002](#), [Revicki 2013](#)}.

Additional analyses will be conducted on all PRO data, including absolute scores and changes from baseline for all items and subscales of the FACT-Anemia instrument, EQ-5D-5L instrument, and PGIS/PGIC at each assessment time point for each arm.

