6.1.3. Analysis of the Primary Efficacy Endpoints

The primary analysis of CR rates was done at the 1st interim efficacy analysis (data cut date: 12Aug2022) based on the first 348 randomized patients in the ITT Analysis Set using the Cochran-Mantel-Haenszel (CMH) test, stratified by the stratification factors at randomization. The odds ratio comparing the 2 arms adjusted for the stratification factors was presented along with 95% confidence interval (CI).

The point estimate of the CR rate and the corresponding 2-sided exact 95% CI based on the Clopper-Pearson method was provided for each arm. Patients, who are randomized but have no on-study response assessment or receive any new anticancer therapy including SCT prior to achieving CR, are considered as non-responders.

If the CR rate of experimental arm is higher than that of control arm and 2-sided p-value from the stratified CMH test using SAS procedure freq is less than 0.03, the null hypothesis of CR rate in Section 6.1.2 would be rejected and the superiority of experimental arm to control arm in terms of CR rate is established.

The primary analysis of OS will compare the OS distributions of two treatment groups using the stratified log-rank test, stratified by the stratification factors at randomization for the ITT Analysis Set. Medians, Q1, Q3 of the OS distributions, and the proportion of patients who are alive at 6, 12, 18 and 24 months from randomization will be estimated along with corresponding 95% CIs using the Kaplan-Meier method. Kaplan-Meier curves will be provided by treatment group.

If the median survival time of experimental arm is longer than that of control arm and two-sided p-value from the stratified log-rank test using SAS procedure Lifetest is less than the cutoff p-values based on observed number of OS events by the data cutoff date as mentioned in Section 2.1, the null hypothesis of OS in Section 6.1.2 will be rejected and the superiority of experimental arm to control arm in terms of OS is established.

In addition, the HR between the 2 treatment groups and its 95% CI will be estimated using the Cox proportional hazards regression model stratified by the stratification factors. For pre-specified non-binding futility analysis boundary of HR=0.95 at the second interim analysis if CR was not statistically significant, the HR from the Cox model will be used to check whether the futility boundary has been crossed or not.

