6.4.2. Analysis of Patient-Reported Outcome Data

In addition to the analyses specified in Section 6.2 for the secondary PRO endpoint, exploratory analyses comparing the effects of magrolimab + azacitidine versus placebo + azacitidine on health-related quality of life will be performed on the 4 PRO measures: FACT-Anemia, EQ-5D-5L, PGIS, and the PGIC. Analyses will be based on the ITT Analysis Set.

FACT-Anemia

- FACT-G: Mean total score and subscale scores at baseline and all follow-up timepoints will be summarized by treatment arm. The FACT-G consisits of the physical, social/family, emotional, functional subscales.
- FACT TOI-An: Mean total score and subscale scores at baseline and all follow-up timepoints will be summarized by treatment arm. The FACT TOI-An consists of the physical, functional and anemia symptoms subscales.
- FACT TOI-F: Mean total score and subscale scores at baseline and all follow-up timepoints will be summarized by treatment arm. The FACT TOI-F consists of the physical, functional and fatigue subscales.
- FACT-F: Mean total score and subscale scores at baseline and all follow-up timepoints will be summarized by treatment arm. The FACT-F consisits of the physical, social/family, emotional, functional and fatigue subscales.

EQ-5D-5L

The EQ-5D-5L data will be summarized by treatment group and visit as the following:

- A health profile: summary statistics will be provided, including number and percentage of patients who report each response category for the 5 dimensions (mobility, self-care, usual activity, pain/discomfort, and anxiety/depression).
- A self-perceived current health score: calculated from patient level EQ VAS responses (continuous variable). Descriptive statistics will be provided.

PGIC/PGIS

The proportion of patients who report each response category on the PGIC and PGIS at scheduled time-point will be summarized by treatment group. Descriptive statistics will be calculated for PGIC and PGIS at scheduled time-point. The mean and change from baseline on the PGIS to each subsequent assessment may be summarized.

Additional exploratory analyses may be conducted and documented in a separate PRO SAP.

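### The FACT-Anemia response test stratifies by randomization factors only; prespecifying adjustment for the collected baseline score would gain modest precision at almost no cost

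*SAP*

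**What the plan says.** FACT-Anemia response is the eighth and last key secondary endpoint in the testing order (protocol 8.3.1, SAP 2.1). Its two-sided alpha is 0.05 if the CR hypothesis was rejected and 0.02 if not.

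- **Test.** SAP 6.2.2.1: "FACT-Anemia response rate will be evaluated in a similar manner as the CR rate". Protocol 8.7 places it in the ITT Analysis Set and adds "The analysis method is similar to that of the CR rate". The CR method in SAP 6.1.3 is the "Cochran-Mantel-Haenszel (CMH) test, stratified by the stratification factors at randomization".
- **Definition.** SAP 6.2.1: "The minimal clinically meaningful difference of 7.0 as suggested in the referenced literature will be used as cutoff for clinically meaningful improvement". No visit is named. Participants who "have no baseline or no postbaseline FACT-Anemia questionnaire assessment" count as non-responders, as do those who start new anticancer therapy before responding.
- **Baseline data.** Protocol Table 3 schedules the questionnaires on Cycle 1 Day 1. For the scales derived from FACT-Anemia, SAP 6.4.2 plans descriptive output: "Mean total score and subscale scores at baseline and all follow-up timepoints will be summarized by treatment arm".
- **Covariates.** SAP 3.3 allows baseline covariates in efficacy models at the sponsor's option if prognostic characteristics are imbalanced, and labels such models sensitivity analyses. It does not name FACT-Anemia.

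**The concern.** CR is a status reached on treatment, so the randomization factors are natural strata for it. FACT-Anemia response has a different structure because it is a dichotomized change score. Unless follow-up tracks baseline one for one, participants with low baseline scores respond more often. The baseline score is then a predictor of the outcome, it is already in the database, and it is needed to derive response. The confirmatory test nevertheless uses it only for that derivation.

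At stake is the precision of one alpha-controlled quality-of-life comparison, should the hierarchy reach it.

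**Working it through.** **1. The plan's own figure.** No power or response rate is stated for FACT-Anemia. The inherited method has a stated power for CR: 95% with 348 participants, 20% versus 39%, two-sided 0.03. With 174 per arm and pooled rate 0.295:

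- null SE = √(2×0.295×0.705/174) = 0.0489
- alternative SE = √((0.20×0.80 + 0.39×0.61)/174) = 0.0478
- (0.19 − 2.170×0.0489)/0.0478 = 1.75, so power is 96.0%

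The plan's figure stands, and nothing below changes it.

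**2. Link between response and baseline.** Assume equal SDs at baseline and follow-up, with correlation ρ. The correlation of change with baseline is −√((1−ρ)/2). Cutting change at 7 multiplies this by φ(z)/√(p(1−p)), where z = 7/(SD√(2(1−ρ))) and p is the response probability with no mean shift. For SD 25 and ρ = 0.5:

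- z = 7/25 = 0.28, p = 0.390, φ(z) = 0.384
- correlation of response with baseline = −0.5×0.384/0.488 = −0.39
- variance explained = 0.39² ≈ 15%

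At ρ = 0.85 the same steps give −0.21 and about 4%. The link is therefore weak to moderate.

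**3. Ceiling.** Protocol 5.1.9.1: "The FACT-Anemia questionnaire is a 47-item instrument", with items scored 0 to 4. The maximum is 47×4 = 188, so a 7-point gain is impossible only above 188 − 7 = 181. The link comes mainly from regression to the mean.

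**4. Precision.** Simulation of 520 participants (260 per arm), 600 runs per row. All inputs are assumed: true shift 5 points, and response counted at one visit or at the best of four because the SAP names none. The strata-only CMH test is compared with a standardized risk difference from a logistic model with continuous baseline. The variance ratio is adjusted over unadjusted, and the gain in effective N is 1/ratio − 1 (for example 1/0.864 − 1 = 15.7%).

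| ρ | SD | Visits | Set to non-responder | Variance ratio | Effective N | Power at 0.05, CMH → adjusted |
|---|---|---|---|---|---|---|
| 0.3 | 25 | 1 | 10% | 0.810 | +23.4% | 26.8% → 32.5% |
| 0.3 | 25 | 4 | 10% | 0.795 | +25.8% | 27.7% → 33.7% |
| 0.5 | 25 | 1 | 10% | 0.864 | +15.7% | 37.7% → 44.0% |
| 0.5 | 25 | 4 | 10% | 0.851 | +17.6% | 36.5% → 42.3% |
| 0.7 | 25 | 1 | 10% | 0.915 | +9.3% | 55.0% → 58.8% |
| 0.7 | 25 | 4 | 10% | 0.905 | +10.5% | 57.0% → 63.7% |
| 0.85 | 25 | 1 | 10% | 0.957 | +4.5% | 82.8% → 85.3% |
| 0.85 | 25 | 4 | 10% | 0.944 | +5.9% | 86.5% → 89.2% |
| 0.7 | 20 | 1 | 10% | 0.920 | +8.7% | 76.3% → 80.0% |
| 0.5 | 25 | 1 | 25% | 0.899 | +11.3% | 29.8% → 32.7% |
| 0.7 | 25 | 4 | 25% | 0.939 | +6.5% | 39.8% → 42.0% |

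Gains run from 2.2 to 6.7 points. With no treatment effect (1,500 runs), rejection was 5.3% for CMH and 5.6% adjusted at 0.05, and 2.2% for both at 0.02. These runs treated the strata as unrelated to response and every baseline as known. The Monte Carlo error of a single power near 50% is √(0.25/600) = 2.0 points.

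**5. With missing baselines.** Further simulation (520 participants, SD 27, ρ 0.5-0.7, 1 or 6 visits, 10-25% set to non-responder, 5% missing baseline) used either a logistic model with mean-filled baselines or CMH on baseline tertiles with collapsed strata. Power rose by about 0.5 to 8 points, with type I error near 5%.

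**6. Crossing tertiles with every stratum.** The randomization factors give 2×3×2 = 12 strata. Tertiles plus a missing level make 12×4 = 48 cells, on average 520/48 ≈ 11 participants each. Under assumed stratum shares about 28 of the 48 held fewer than 10. A full cross of tertiles with the 12 strata changed effective sample size by −1% to +10%, against +5% to +15% with the randomization strata collapsed.

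**The case against.** The strongest reply is that nothing is wrong. Stratifying by the randomization factors is the plan's uniform rule for its comparative response and time-to-event tests, and it gives a valid test. That stands: this is a point about efficiency.

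A reader might infer that a chance baseline difference passes straight into the response-rate difference. It does not. With SD 27 and 260 per arm, a one-SE baseline difference is 27×√(2/260) = 2.4 points, or 0.09 SD. With a response-baseline correlation of 0.25-0.40 and a response SD near 0.49, the response difference moves by 0.09×0.25×0.49 to 0.09×0.40×0.49, about 1 to 2 percentage points. Its standard error is about √(2×0.24/260) = 4 points, and the unadjusted test already allows for such variation.

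A reader might also infer that baseline strongly determines who can gain 7 points, or that the plan ignores it. The documents contain no figure for the first, and the ceiling touches only scores above 181 of 188. On the second, the score enters the definition of response, and SAP 3.3 permits optional covariate models after an imbalance. Those models leave the tested analysis unadjusted, however, and a covariate chosen after seeing an imbalance is weaker than a prespecified one.

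Finally, the non-responder rule dilutes the gain. With 25% set to non-responder on top of missing baselines, the 48-cell CMH changed power by only −0.5 to +1.6 points. This stands, and it is why the fix avoids that cross.

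**Conclusion.** The point holds as a minor, optional improvement. The planned test is valid, and the documents support no claim of bias, inflated type I error or a wrong figure. It gives up some precision that a variable already collected could supply: roughly 0.5 to 8 power points under the assumed ranges, less when many participants are non-responders by rule. The size cannot be fixed more closely, because the SD, the correlation, the response rate and the non-responder rate are all assumptions. The practical reach is narrow, since the test is formal only if OS and the seven earlier key secondary endpoints all succeed.

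**What to change.** Before data finalization for the second interim analysis, amend SAP 6.2.2.1 for FACT-Anemia response only:

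- **Preferred.** Logistic regression with treatment, the three randomization factors as main effects and continuous baseline FACT-Anemia score, reporting a standardized risk difference. Keep participants without a baseline score in the ITT analysis as non-responders and set their covariate to the pooled blinded mean. Do not add a missing indicator: they are all non-responders by definition, so it would separate completely.
- **Alternative.** CMH stratified by pooled baseline tertiles, with missing as its own level, crossed with a prespecified reduced set of randomization strata. The missing level adds no information but keeps everyone in the analysis.
- Keep the current CMH test as a sensitivity analysis.
- Record the change in SAP Section 10, which now declares no departures from the protocol, because protocol 8.7 names the CR method.

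The cost is a few lines of SAP text. The logistic model yields a conditional odds ratio, which needs the standardized difference beside it. No new data are required, and the endpoint, alpha and hierarchy do not change.
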